1. BACKGROUND AND PROJECT RATIONALE

In 2013 the QualiCCare association was founded, the purpose of which, according to the statutes, is to develop concrete and pragmatic measures for the treatment of the chronically ill in the extended primary care through the interprofessional cooperation of all stakeholders. This involves coordination with the national strategies in the field of chronic diseases (NCD, CVSD, etc.), as well as a continuous review of the measures developed in the "real-life" setting, i.e. in primary care.

Based on international guidelines, the QualiCCare 2011-2013 project identified essential treatment elements for which there is potential for improvement in Switzerland compared with best practice examples. Four priorities were identified for diabetes mellitus type 2: (1) screening and diagnosis, (2) self-management training, (3) drug therapy of diabetes and co-risk factors, and (4) control and treatment of macrovascular and microvascular complications. Specific and pragmatic measures have been developed to improve treatment outcomes. Based on the NCQA recommendations (National Council Quality Assurance) and a best-practice comparison with other countries, developed as part of the QualiCCare project 2011-2013, the Swiss Society for Diabetology and Endocrinology (SGED) developed adapted "criteria for "good" disease management diabetes in primary care" (hereinafter "criteria") for Switzerland. The quality of care for patients with type 2 diabetes can be evaluated by calculating a score determined during the application of the criteria. In two pilot projects, the criteria were followed in a multi-year comparison:

I. Pilot project I: all type 2 diabetes patients of a single primary care practice with several doctors over 3 years;

II. pilot project II: all type 2 diabetes patients in the Chronic Care Management Program in 5 group practices over 2 years.

The aim of the Diabetes Project III is to establish the above-mentioned score in different practice infrastructures. The aim is to record the effect of the score on the quality of treatment and to evaluate its suitability for practical use. The score criteria will additionally include influenza vaccination as an important prevention measure and the drug therapy (oral antidiabetics and/or insulin, antihypertensives, and statins) in order to determine possible comorbidities based on the medication.

At the same time, the present project is also an extension to the previous projects I and II in terms of measuring suitability for practice, as on the one hand a larger number of practices apply the criteria and on the other hand different practice structures are included in the project.

In accordance with Art. 5 and Art. 10 of the Human Research Act (HFG), this project serves to improve public health and meets scientific requirements. The responsible scientific advisory board is independent in its decisions and bases them on the latest scientific findings in this field. In accordance with Art. 7 of the "Ordinance on Human Research Excluding Clinical Trials" (HFV), this is accompanying research of risk category A.

2. PROJECT OBJECTIVES, DESIGN AND STATISTICS

2.1 Hypothesis and primary objective

By implementing evidence-based measures (by means of score), the treatment quality (corresponds to an improvement of the score) of patients with diabetes mellitus type 2 in the "Real World Setting" can be improved within 12 months.

The score can be used in different practice infrastructures and does not result in differences in treatment quality.

2.2 Primary and secondary endpoint(s)

Primary endpoint:

Change in score after use of this method to document care of patients with diabetes mellitus type 2 (baseline vs. 12 months)

Secondary endpoints:

Evaluation of the practicability of the score in different GP practice structures

Comparison of diabetes care (i.e. scores) between different organisational forms of practices (individual practices, group practices, practice chains)

Evaluation of the software for the evaluation of the score.

2.3 Project design

Prospective, non-randomised study without control group.

2.4 Statistics and methodology

Statistical evaluation concept:

Primary endpoint:

Comparison of score baseline vs. 12 months using paired t-test.

Secondary endpoints:

Comparison of score changes between individual practices and practice networks using unpaired t-test.

Evaluation of the evaluation forms with regard to practical suitability and software by means of descriptive statistics.

In the previous two pilot studies, a measurable improvement in treatment quality could be measured in one and five primary care practices, respectively, with an increase in the score to 58 + 20 points. In order to achieve the goal of a relevant improvement of the overall score by a total of 10 points (from 56 to 66 points), 27 centres must be recruited with a significance level of 0.05 and a power of 80% (1). At a dropout rate of 10%, we will recruit 30 centers.

Methodology

Information of the primary care practices regarding the background and goal of the project by means of a letter and informative documentation.

Recruitment of primary care practices, divided into three different practice organisations (individual practices and group practices run on a private basis and with financial autonomy, as well as forms of joint practices with employed physicians without financial autonomy).

A signed contract between QualiCCare and participating primary care practices regulates the collaboration.

Procedure:

A baseline documentation takes place retrospectively from the training/workshop for the past 12 months, and a second, prospective documentation of the treatment is done during the following 12 months.

Training of the participating GPs and practice coordinator on the project including evaluation software, data entry and background to the criteria.

Documentation of the treatment quality of all patients with diabetes mellitus type 2 in a practice structure that meets the inclusion criteria according to the score criteria (baseline).

After 12 months, the treatment quality of the included patients with diabetes type 2 is recorded again using the same score.

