3.2 Recruitment, screening and informed consent procedure

The general practitioners will be invited to participate by post with a letter and information about QualiCCare and the project. There will be 10 practices per organisational structure. Each practice documents its diabetes patients based on their patient dossiers according to inclusion criteria. In order to participate in the study, patients will be informed about the study at the next follow-up and asked to sign a letter of consent to participate. A document will be available to the practices for patient information. Patients will be given sufficient time to decide whether to participate in the study.

The practice will receive CHF 50.00 per participating patient with documented score and free use of the diabetes management tool during the duration of the project. The medical services will be reimbursed according to usual tariff, Tarmed. In addition, the practice receives an evaluation of its practice performance compared to the overall collective.

The patient does not receive any financial compensation.

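### Three practice forms are to be compared (2.2), but the only between-form test (2.4) has two groups, one of them undefined, and it cannot support the no-difference statement in 2.1

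*Combined protocol and SAP*

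**What the plan says.** **Aim.** Section 1 says: "The aim of the Diabetes Project III is to establish the above-mentioned score in different practice infrastructures". It gives as one reason for extending the pilot work that "different practice structures are included in the project".

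**Hypothesis.** Section 2.1, under the heading that covers the primary objective, states: "The score can be used in different practice infrastructures and does not result in differences in treatment quality".

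**Endpoint.** Section 2.2 lists as a secondary endpoint: "Comparison of diabetes care (i.e. scores) between different organisational forms of practices (individual practices, group practices, practice chains").

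**Recruitment.** The Methodology part of 2.4 plans "Recruitment of primary care practices, divided into three different practice organisations". The third of these is described there as "forms of joint practices with employed physicians without financial autonomy", not as chains. Section 3.2 adds: "There will be 10 practices per organisational structure".

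**Analysis.** The statistical concept in 2.4 gives one test between forms: "Comparison of score changes between individual practices and practice networks using unpaired t-test". The descriptive statistics planned in 2.4 concern the evaluation forms on practicability and software, so they do not cover the comparison of forms. The other planned test, the paired t-test for the primary endpoint, compares time points and not forms.

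**The concern.** The endpoint has three groups and the test has two. The second group, *practice networks*, is not one of the three forms in 2.2 or 2.4, so an analyst must decide which practices belong to it, possibly after seeing the data. That decision settles which differences the test can show.

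Two further details are open. Section 2.2 speaks of scores and 2.4 of score changes, which are different outcomes. Section 2.4 also does not say whether the unit is the patient or the practice. With ten practices per form and the more than 50 patients per practice in 3.1, that means 10 units per form or more than 10 × 50 = 500. A patient-level t-test that ignores practice would treat those patients as independent.

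The no-difference statement in 2.1 is a separate matter. It has no margin, interval rule or test of its own, and the only between-form test is a test for a difference.

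At stake is whether the project can report what 2.2 promises on a question that Section 1 gives as a reason for the project.

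**Working it through.** **The plan's own figures.** No sample size or power is stated for the comparison between forms. The 27 centres in 2.4 and 3.1 are for the before-after change of 10 points (56 to 66). A paired t-test with SD 20, difference 10 and one-sided 0.05 needs n = 27 (power 81.2%). The sidedness and that SD are inferred, since the plan states neither for this calculation. Then 27 / 0.9 = 30 = 3 × 10 practices.

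**Why two groups cannot serve three forms.** Three means carry two independent contrasts. A two-sample test estimates one, so no definition of *practice networks* can compare all three forms separately.

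**What each reading tests.** Let one form differ by 10 points from the other two, which are equal. The 10 is borrowed from the before-after target; the plan gives no between-form difference. No SD is needed for this table (absolute contrasts).

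| Reading of the test | Individual differs | Group differs | Chains differ |
|---|---|---|---|
| A. Individual v group and chains merged | 10 | (10 + 0)/2 = 5 | (0 + 10)/2 = 5 |
| B. Individual v chains, group left out | 10 | 0 | 10 |
| C. Individual v group, chains left out | 10 | 10 | 0 |
| D. Individual and group merged v chains | (10 + 0)/2 = 5 | (0 + 10)/2 = 5 | 10 |

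Reading D is possible because the Methodology in 2.4 groups the two privately run, financially autonomous forms together against the form with employed physicians.

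**Power, as illustration only.** The unit is the practice, with 10 per form, two-sided 0.05 and pooled variance. The SD of a practice's score change is assumed to be 7.5 / 10 / 15, because the plan gives none (the 15 in 3.1 refers to the total score). Worked at SD 10:

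- 10 v 20, contrast 10: noncentrality 10 / (10 × √(1/10 + 1/20)) = 2.58 on 28 df.
- 10 v 10, contrast 10: 10 / (10 × √(2/10)) = 2.24 on 18 df.
- Three-form F-test: λ = 10 × (6.67² + 2 × 3.33²) / 10² = 6.67 on 2 and 27 df.

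| Situation | SD 7.5 | SD 10 | SD 15 |
|---|---|---|---|
| 10 v 20, full contrast 10 (A, individual differs; D, chains differ) | 91.3% | 70.3% | 38.3% |
| 10 v 20, diluted contrast 5 (A or D, a form inside the merged group differs) | 28.0% | 19.1% | 11.7% |
| 10 v 10, contrast 10 (B or C, a tested form differs) | 80.5% | 56.2% | 29.2% |
| 10 v 10, contrast 0 (B or C, the omitted form differs) | 5% | 5% | 5% |
| Three-form F-test, whichever form differs | 83.8% | 58.1% | 28.8% |

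The diluted row is by simulation (200,000 runs), because merging unequal forms also widens the spread within the merged group. The rows for C and D follow by symmetry from B and A.

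**Precision of the alternative.** The half-width of a pairwise 95% interval from the three-form model is t(0.975, 27 df) × SD × √(2/10) = 2.052 × SD × 0.447 = 6.9 / 9.2 / 13.8 points.

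**The no-difference statement.** With 10 v 10 practices and an assumed SD of 15, a true 10-point difference is missed 100 − 29 = 71% of the time; at SD 10, 100 − 56 = 44%. A non-significant result is therefore compatible with a difference as large as the improvement that 2.4 calls relevant.

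**The case against.** The best defence is that this is an unpowered secondary comparison in an uncontrolled, non-randomised project, that most readers would take *networks* to mean every non-individual practice, and that the merged test is then a sensible choice. Part of this stands. If only individual practices differ, the merged test is more powerful than a three-form F-test (70.3% against 58.1% at SD 10). It still does not deliver the endpoint in 2.2, and 2.4 itself separates group practices with financial autonomy from practices without it.

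The power figures also carry limited weight. They rest on an assumed SD and a borrowed difference, and the plan claims no power here. The point rests on the text and on the contrast table.

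Some stronger readings are tempting but not supported:

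- *The planned test always loses when group practices differ, or never sets them against chains.* Under reading C a group-practice difference is tested at the full 10 points. Under reading D group practices are set against chains, though pooled with individual practices. What holds is that no reading gives group against chains as a separate pair.
- *The investigators will read non-significance as no difference.* No section says so. The documents show only that the planned test cannot establish the statement in 2.1 and that no other rule is given.
- *The main result is affected.* The paired t-test for the primary endpoint does not depend on how the forms are grouped.

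**Conclusion.** The concern holds in this form: the between-form analysis in 2.4 cannot produce the three-form comparison in 2.2, and its second group is undefined. For a single form differing by 10 points, the contrast actually tested is 10, 5 or 0 points, depending on which form it is and how *practice networks* is read. The differing outcome wording and the unstated unit add to the ambiguity.

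Separately, the no-difference statement in 2.1 has no margin or interval rule, and a non-significant difference test cannot establish it.

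Confidence is high for the textual mismatch and for the contrasts, which need no SD. The power percentages are illustrations under assumed SDs of 7.5 to 15. This should be put right before analysis, but it concerns a secondary endpoint only.

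**What to change.** In 2.4:

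- Use the three forms of 2.2 with one label each throughout, and define or delete *practice networks*.
- Compare score change across the three forms with a one-way linear model of practice mean change, or with a patient-level mixed model that has a random effect for practice.
- Report the three pairwise differences with 95% confidence intervals, as estimates and not as multiplicity-adjusted tests. Three unadjusted tests at 0.05 would carry a family-wise error of up to about 1 − 0.95³ = 14%, on an independence approximation.
- If individual against other practices is of special interest, keep it as a named, defined additional contrast.
- State that a non-significant result will not be read as no difference.

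Make the outcome wording in 2.2 and 2.4 agree, and restate the sentence in 2.1 as a descriptive estimation aim.

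**Cost.** Recruitment, data collection and the primary test stay as they are. If the merged reading was meant and only individual practices differ, power falls from 70% to 58% at an assumed SD of 10, unless that contrast is kept. The no-difference claim becomes descriptive. Because 2.1 is the hypothesis section, the rewording may need ethics committee approval under 4.5 if it counts as substantial.

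### The secondary endpoint compares scores between practice forms, but the only analysis planned for it compares score changes, so the stated endpoint is not analysed

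*Combined protocol and SAP*

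**What the plan says.** Section 2.2 names the primary endpoint as the change in score from baseline to 12 months. In the same list it gives a secondary endpoint in different terms: "Comparison of diabetes care (i.e. scores) between different organisational forms of practices (individual practices, group practices, practice chains").

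Section 2.4 assigns the tests. The primary endpoint gets "Comparison of score baseline vs. 12 months using paired t-test". The between-form endpoint gets "Comparison of score changes between individual practices and practice networks using unpaired t-test". The remaining secondary endpoints, on practicability and software, are descriptive.

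Two other places bear on what is meant by quality of care. Section 1 says "The quality of care for patients with type 2 diabetes can be evaluated by calculating a score determined during the application of the criteria". Section 2.1 puts the hypothesis on practice forms as "The score can be used in different practice infrastructures and does not result in differences in treatment quality", and its preceding sentence speaks of "the treatment quality (corresponds to an improvement of the score) of patients with diabetes mellitus type 2".

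Section 2.3 describes a non-randomised study without a control group. Section 3.2 plans ten practices per organisational form and promises each practice feedback against the whole collective. That feedback is not a comparison between forms.

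**The concern.** The endpoint asks how the score compares between forms. The analysis asks how the improvement in score compares between forms. The wording does not look like loose shorthand, because section 2.2 uses both terms and gives change to the primary endpoint and scores to this one.

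The difference matters because practices belong to a form by their organisation, not by allocation, so nothing makes the starting levels equal. If two forms improve by the same amount, a test of changes shows nothing, however far apart their scores are at both time points. A reader who takes that result as the answer to the section 2.2 endpoint could conclude that care is alike across forms when the analysis never examined it. Conversely, unequal changes may accompany a narrowing gap in scores, and the change result alone would not show this.

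**Working it through.** **The plan's own figure.** The plan gives no sample size or precision for this comparison. Its one calculation, "27 centres must be recruited with a significance level of 0.05 and a power of 80" per cent, concerns the 10-point improvement (56 to 66). It can be reproduced with a paired t-test, a difference of 10, a one-sided 0.05 level and an SD of 20, reading the unlabelled 20 in section 2.4 as an SD: n = 27, power 81.2%. A two-sided test with the same inputs needs 34. Inflating for 10% dropout gives 27/0.9 = 30. Nothing below depends on this.

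**Algebra.** Let B and T be the mean baseline and 12-month scores in forms 1 and 2. The planned contrast is

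(T1 − B1) − (T2 − B2) = (T1 − T2) − (B1 − B2).

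If the gap is the same size at both times, T1 − T2 = B1 − B2 = G, the contrast is G − G = 0 for every value of G. This holds for any SD and any number of practices.

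**Two illustrations.** All means are assumed; the documents give no scores by form.

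- Equal improvement: form A 50 to 60, form B 66 to 76. Difference in change (60 − 50) − (76 − 66) = 0. Gap at 12 months 76 − 60 = 16.
- Converging scores: form A 50 to 62, form B 66 to 70. Difference in change (62 − 50) − (70 − 66) = 12 − 4 = 8. The gap falls from 66 − 50 = 16 to 70 − 62 = 8.

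**How the two tests behave.** Assumptions:

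- The analysis uses practice means. The plan does not state the unit.
- There are 10 individual practices against 20 others, from ten per form, with the other two forms together taken as the networks.
- The between-practice SD is 15 to 20. These values are borrowed as a range; the documents give no between-practice SD labelled as such.
- The baseline to 12-month correlation is 0.5, the level is two-sided 0.05, and both groups improve by 10 points.

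For a test of 12-month scores, the standard error is SD × √(1/10 + 1/20) = SD × 0.387, which is 5.81 at SD 15 and 7.75 at SD 20. With a 20-point gap the noncentrality is 20/5.81 = 3.44 or 20/7.75 = 2.58, and the noncentral t with 28 degrees of freedom gives the power. For the change test, the SD of a change is SD × √(2 × (1 − 0.5)) = SD, and the noncentrality is 0.

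| Constant gap | SD | Change test rejects (20,000 simulated trials) | 12-month score test rejects (noncentral t) |
|---|---|---|---|
| 10 | 15 | 4.8% | 38% |
| 10 | 20 | 5.1% | 24% |
| 20 | 15 | 5.1% | 91% |
| 20 | 20 | 5.2% | 70% |

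The change test rejects at its nominal 5% whatever the gap. It carries no information about a constant difference in scores.

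**The case against.** The strongest reply is that section 2.1 points to change. Its first sentence ties treatment quality to an improvement of the score. Its second makes the score the subject and uses causal language: the score does not result in differences. On that reading the question is whether using the tool makes the forms diverge, and a comparison of changes is a sensible way to answer it. This stands. A reader might infer that section 2.1 also concerns the level of the score and that section 2.4 therefore fails both sections. The documents do not establish that: section 1 supports a level reading of quality, section 2.1 leans towards change, and the text is ambiguous. Under the causal reading, reporting unequal improvement in the second illustration as a difference between forms would be fair.

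It can also be said that a 12-month gap between non-randomised forms may simply be carried over from baseline, so the 12-month score should not govern every statement about quality. That stands too, and it is why the baseline difference has to be shown with it.

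Finally, the endpoint is secondary, the gaps are invented, and the primary test and sample size are untouched. All true. None of it supplies a between-form comparison of scores, which section 2.2 asks for and no section plans.

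**Conclusion.** The point holds as a mismatch between section 2.2 and section 2.4: the stated endpoint is the score by form, and the only planned analysis is of the change in score. By algebra, that analysis cannot detect a constant gap of any size. In the assumed example a 16-point gap at 12 months goes with a difference in change of 0. The table's rejection rates rest on the assumed SDs, correlation, gaps and 10 versus 20 split; the cancellation does not.

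Three stronger conclusions are not supported. A reader might infer that the forms do differ widely in quality; no section gives scores by form, so a gap is only a possibility. A reader might infer that the plan will declare the forms equal; it sets no rule for doing so. And the SD of 15 in section 3.1 is stated for the total score in the individual practices, so it is not a yardstick for calling a difference between forms large.

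The collapse of three forms into two groups and the absence of an equivalence margin are separate matters. Settling either would not change which variable is analysed.

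**What to change.** In section 2.4, for the section 2.2 endpoint, add estimates of the between-form differences in baseline score and in 12-month score, each with a 95% confidence interval. Keep the comparison of changes beside them as a separately named analysis addressed to the section 2.1 hypothesis. State the reporting language in advance: results on change are described as similar or different improvement; results on level are described as differences in score, read with the baseline difference, and not as effects of the tool.

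The sponsor could instead reword the section 2.2 endpoint as score changes. That would remove the inconsistency but would leave the comparison of care between forms unanswered, although the data for it are in hand.

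The cost is some SAP wording and a few more secondary estimates to report; both scores are already collected. The estimates will be imprecise. On the assumptions above, the 95% interval for a difference in 12-month score with 10 versus 20 practices has a half-width of 2.048 × 5.81 = 11.9 points at SD 15 and 2.048 × 7.75 = 15.9 at SD 20. The intervals should therefore be the main result, not the p-values.

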6.2 Data recording and source data

The patient data is entered in encrypted form: Only the patient's gender and year of birth are entered. Central data analysis does not allow any conclusions to be drawn on the names of patients. For quality assurance purposes, a patient number is listed which could be used for queries to the practice in the event of inconsistencies in the entry (e.g. invalid value entry). The patient number is password-protected and can only be accessed by the staff of the corresponding practice. The number corresponds to the patient file in the practice, i.e. the medical assistant assigns the patient number in the documentation or takes it from the patient file.

The data recorded in the software is stored in a cloud of the independent hosting company Atos (www.de.atos.net/de-de/home.html) in D-Fürth. The patient data is only accessible to the physician (and his practice staff). The data backup is secured in accordance with the European Data Protection Act and complies with Swiss data protection regulations.

Project data will be handled with uttermost discretion and is only accessible to authorised personnel who require the data to fulfil their duties within the scope of the research project. On the CRFs and other project specific documents, subjects are only identified by a unique subject number.

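### Non-randomised practice forms are compared by an unadjusted t-test although age, sex and medication are recorded, so where patient mix affects the change it can mimic or mask a difference between forms

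*Combined protocol and SAP*

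**What the plan says.** The combined protocol and SAP describes the design in 2.3 as "Prospective, non-randomised study without control group". Section 3.2 sets the recruitment target by form: "There will be 10 practices per organisational structure". The second hypothesis in 2.1 is that "The score can be used in different practice infrastructures and does not result in differences in treatment quality", and 2.2 lists as a secondary endpoint "Comparison of diabetes care (i.e. scores) between different organisational forms of practices (individual practices, group practices, practice chains".

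The only inferential analysis of practice form is in 2.4: "Comparison of score changes between individual practices and practice networks using unpaired t-test". No covariate, stratification or regression model appears anywhere in the plan.

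Patient characteristics are nevertheless collected. On identifying details, 6.2 states "Only the patient's gender and year of birth are entered". Section 1 adds drug therapy (antidiabetics, antihypertensives and statins) to the score criteria "in order to determine possible comorbidities based on the medication". No analysis uses these data.

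**The concern.** A practice's form exists before the study and is not assigned, so nothing balances the patients of individual practices against those of the other forms. The plan also leaves room for unequal selection. Section 3.1 counts the nine months of prior care per physician, but per practice in group practices, and it lets the doctor exclude patients for frailty or end of life. Section 3.3 accepts that patients with psychosocial difficulties may be left out and calls this unimportant because the collective matters. That does not help when collectives are compared with each other.

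If older or more complex patients improve by more or less than others, a difference in their share between forms shifts the crude difference in change. A significant result could then be patient mix, and a real difference could be cancelled and read as support for the hypothesis in 2.1.

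**Working it through.** **The plan's own figure.** No sample size or power is given for the comparison of forms. The 27 centres concern the primary endpoint. They reproduce with a one-sided paired t-test, a gain of 10 points (56 to 66) and SD 20 (reading the pilot figure of 58 and 20 as mean and SD): n = 27, power 81.2%. Then 27 / 0.9 = 30 after 10% dropout. This has no bearing on the present point.

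**Inputs from the documents.** 10 practices per form (3.2); more than 50 patients per practice, taken as 50 (3.1); test on changes (2.4).

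**Assumptions, because the documents give no figures.**
- Networks means group practices plus chains, which gives 10 v 20 practices. Section 2.4 does not define the term.
- The practice-level SD of the change is 5 to 10.
- The share of complex patients differs between the groups by 10 to 30 percentage points.
- The gap in change between complex and other patients is 1 to 10 points.

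**Bias of the crude difference** = (difference in share) × (gap in change).
- Smallest: 0.10 × 1 = 0.1 points.
- Largest: 0.30 × 10 = 3.0 points.

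**Standard error** = SD × √(1/10 + 1/20) = SD × 0.387.
- SD 5: 1.9 points. SD 10: 3.9 points.
- With 10 v 10 practices the factor is √(1/10 + 1/10) = 0.447, giving 2.2 to 4.5 points.

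**Ratio, 10 v 20.** From 0.1 / 3.87 = 0.03 to 3.0 / 1.94 = 1.55, so from negligible to about 1.5 standard errors.

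**Rejection rate of the crude test with no true form effect** (two-sided 5%). Section 2.4 does not say whether the unit is the patient or the practice, so both are shown:

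| Unit | Assumed SD of change | Bias 1 | Bias 2 | Bias 3 |
|---|---|---|---|---|
| 10 v 20 practices | 5 | 8% | 17% | 32% |
| 10 v 20 practices | 10 | 6% | 8% | 12% |
| 500 v 1000 patients | 15 | 23% | 68% | 95% |
| 500 v 1000 patients | 20 | 15% | 45% | 78% |

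The patient rows treat patients as independent and ignore clustering in practices.

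**Simulation** (2000 runs; 10 v 20 practices of 50 patients; 30% v 50% complex patients; patient SD of change 15, between-practice SD 3; t-test on practice means).
- No form effect, gap 5 points: crude bias about 1.0, rejection 9%.
- No form effect, gap 10 points: crude bias about 2.0, rejection 27%.
- In both, adjustment brings the bias to about 0 and rejection to 4 to 5%.
- True form effect of 2 points opposed by a gap of 10: the crude estimate is about 0 and rejects in 5% of runs. The adjusted estimate is 2.0 and rejects in 28%.

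Two features favour adjustment here. The practice-level SD is only about √(3² + 15²/50) = 3.7, below the 5 to 10 used above, and the confounder is measured in full. Age and sex would capture only part of real patient mix.

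**The case against.** **Change is not level.** The test in 2.4 is on changes. A reader might infer that a form with older or sicker patients would look worse under the same care. For stable differences in level that does not follow, because they cancel within the patient. This stands. What remains is mix that alters the size of the change (for example through room to improve), and any comparison of levels, since 2.2 speaks of scores.

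**The size is assumed.** A gap in change of 10 points equals the whole planned gain. With gaps of 1 to 3 points, the bias is 0.1 to 0.9, under half the smallest standard error. The score items are not in the documents, so whether comorbidity affects the gain cannot be judged. This also stands.

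**Medication may not be a safe covariate.** A reader might infer that medication belongs in the main model because section 1 records it to identify comorbidity. The documents do not support that step. Section 1 lists drug therapy among the score criteria, so it may be part of the outcome; whether it earns points is not stated. The baseline year (2.4) is also care by the same physician or practice, given the nine-month rule in 3.1. Adjusting for it could remove real differences between forms.

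**A crude difference is a legitimate description** of forms with the patients they have. That is a reason to report it, but the hypothesis in 2.1 concerns treatment quality, which a crude difference alone cannot isolate.

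**Adjustment does not turn a non-significant result into evidence of no difference.** This is correct, and the change proposed here does not claim to do so.

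**Conclusion.** The gap is real. Practice forms are not allocated, the only test of them is unadjusted, and recorded patient characteristics have no place in any analysis. Where mix affects the change, or where levels are compared, the result can reflect mix or be masked by it.

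The size and direction of the bias are unknown. The range of 0.1 to 3 points, or negligible to about 1.5 standard errors, is illustrative and rests on the assumed imbalances, gaps and SDs and on the 10 v 20 split. It does not show that the planned comparison will be biased to any given degree. Nor should a reader infer doubt about the main result on this ground: the point concerns a secondary endpoint and the second hypothesis, and leaves the primary before-after comparison untouched.

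**What to change.** In 2.4, replace the unpaired t-test by a patient-level mixed model of score change on practice form, adjusted for age (from year of birth) and sex, with practice as a random effect. Define which practices count as networks; 2.4 names two groups where 2.2 names three forms. Report the adjusted difference with its 95% CI and the crude difference beside it. If score levels are also compared under 2.2, use the same covariates.

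Add baseline-year medication (comorbidity proxy and diabetes-therapy class) only in a sensitivity model. State there that medication is listed among the score criteria and is partly care delivered by the practice, so that this model may over-adjust.

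The cost is a few lines of text and a little extra analysis on data already planned for entry. Residual confounding will remain and should be acknowledged in the report.
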